2.7 Other predictors and confounders

The role of other possible predictors and potential confounders will be investigated. These factors will be evaluated for association with the laboratory test results and association with the primary and secondary outcomes and will include age, sex, diabetes, type of surgery, operation urgency, pre-operative kidney function (estimated Glomerular Filtration Rate; eGFR) and pre-operative HCT. Post-operative platelet count will also be included in all models.

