7.1 A priori expected relationships

For each patient characteristic, the following are likely to be associated with an INCREASED likelihood of CCB.

- Increased age
- Female
- Diabetes yes
- Other>CABG+valve>Valve>CABG

5. Urgent operative priority>elective
6. Decreased eGFR
7. Decreased preoperative HCT
8. Low preoperative platelet count
9. Aspirin+P2Y12 blocker (clopidogrel or prasugrel) >aspirin>no drugs
10. Decreased time from P2Y12 blocker withdrawal
11. Reduced BMI

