7.2 Specific analysis procedure

The approach is to evaluate the separate platforms (Multiplate/preop; ROTEM; TEG; Multiplate/postop) individually in the first instance, and then evaluate whether the inclusion of additional platforms would improve this. The reason for considering groups of variables by platform (rather than simply choosing the 'best' subset of variables) is because there is no cost of using extra variables from one platform, but an extra cost of doing a second test. The specific steps are as follows:

- Step 1 Review the prediction achieved by patient characteristics. Define an optimal model based only on "baseline" covariates⁶. There will be a separate model for
- **any CCB** (intra-operative or post-operative) and
 - **post-op CCB** only
- Comment: We expect these models to be consistent with one another, not least because the majority of events (post-op CCPB events) will be common to both models.*
- Step 2 Review of each test platform to obtain the best model for each, including the baseline covariates:
- pre-operative Multiplate in relation to **any CCB** (this model is interesting in its own right, but from a slightly different perspective, i.e. it allows the care team to make a plan to mitigate the risk of CCB or to prepare to manage it)
 - pre-operative Multiplate in relation to **post-op CCB**
 - post-operative Multiplate in relation to **post-op CCB**
 - post-operative ROTEM in relation to **post-op CCB**
 - post-operative TEG in relation to **post-op CCB**
- Comment: Each of these models will consider all variables for the test/timepoint, i.e. consider the test/timepoint as a "package." The first model stands alone for **any CCB**. For **post-op CCB**, this step will identify which of the latter four models is the best platform for predicting CCB, i.e. provides the best prediction. We hypothesise that the best platform will be one of the post-op platforms because the information from these is more 'proximal' to the outcome for these models, i.e. **post-op CCB**.*
- For the best test/timepoint** (assuming there is one best test), we will also investigate whether a model using test variables that are available early (for the test identified as best) performs as well as a model using the standard test variables available at "test completion."

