⁶ These are: age, sex, diabetic status (n/y), cardiac procedure (CABG only, CABG + valve, valve alone, other), operative priority (elective, urgent), eGFR, preoperative HCT, treatment group, time since withdrawal (anti-platelet group), body mass index (BMI), preoperative platelet function and participation in another clinical study.

- Step 3 Test whether the addition of one of the other (post-operative) platforms improves this best model for **post-op CCB**. In practice, this is likely to be a test of whether Multiplate-post improves prediction compared to either ROTEM or TEG (or, adding ROTEM or TEG to Multiplate-post, since ROTEM and TEG are assessing similar mechanisms and Multiplate is assessing different ones). The combination of ROTEM and TEG together will not be considered.
- For the test/timepoint** added at Step 3 (assuming that there is one), we will also investigate whether a model using test variables that are available early (for the test/timepoint added at Step 3) performs as well as a model using the standard test variables available at “test completion.”
- Step 4 Test whether the addition of the pre-operative Multiplate platform improves the model identified in Stage 3.
- If Multiplate-pre** is added at Step 4, we will also investigate whether a model using test variables that are available early for Multiplate-pre performs as well as a model using the standard test variables available at “test completion.”

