7.3 Model fitting

Models will be fitted first for the standard time frame. Then, models will be fitted for the rapid time frame (see [Table 2.6.3](#)), testing whether this results in a “significant” deterioration in prediction. Comparing rapid and standard time frames is interesting because there may be a trade-off between potential benefits of earlier decision making (e.g. allows definitive treatment to be provided more quickly, thereby preventing blood loss) vs. potential harms (e.g. somewhat less good prediction).

The contribution of all of these baseline characteristics to the prediction of CCB were incorporated into a single score which was forced into models of laboratory predictors with a coefficient of 1.00 in order to enable comparisons between different models based on the various laboratory test platforms.

All laboratory measures from a platform were included for each model, with multivariable fractional polynomial techniques used to investigate the linearity of terms. All transformations and centering found to improve the fit of the models were implemented. Backward elimination was undertaken to select the final models with a threshold of inclusion of 0.05 and exclusion of 0.10. Initial models only considered the standard test results (see Table 2); subsequently the ‘early phase’ alternatives were considered for any terms that significantly contributed to the model.

The following models were constructed:

- **Model 2A:** pre-operative Multiplate in relation to **any CCB**
- **Model 2B:** pre-operative Multiplate in relation to **post-op CCB**
- **Model 2C:** post-operative Multiplate in relation to **post-op CCB**
- **Model 2D:** post-operative ROTEM in relation to **post-op CCB**
- **Model 2E:** post-operative TEG in relation to **post-op CCB**

Each model was then compared to a baseline model containing only the baseline characteristics in order to evaluate the contribution of the selected laboratory test results to the prediction of CCB. These are presented as receiver operating characteristic (ROC) curves.

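### Footnote 6 puts pre-operative platelet function in the baseline score where section 7.1 has platelet count; read literally, pre-operative Multiplate is tested against a comparator that may already contain it

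*SAP*

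**What the plan says.** Step 1 of SAP section 7.2 reads "Define an optimal model based only on 'baseline' covariates", and footnote 6 lists those covariates. The list closes with "body mass index (BMI), preoperative platelet function and participation in another clinical study". No assay, parameter or platform is given for the platelet function item.

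Section 7.1 lists the patient characteristics expected to relate to clinical concern about bleeding (CCB). Its platelet item is "Low preoperative platelet count".

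The footnote 6 list feeds everything downstream. Step 2 is headed "Review of each test platform to obtain the best model for each, including the baseline covariates". Section 7.3 says that the baseline characteristics were "incorporated into a single score which was forced into models of laboratory predictors with a coefficient of 1.00", and that each model was then compared with a model holding only the baseline characteristics. The first model on the list is "pre-operative Multiplate in relation to any CCB"; Model 2B relates the same platform to post-operative CCB. Step 4 is to "Test whether the addition of the pre-operative Multiplate platform improves the model identified in Stage 3".

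Section 2.7 has a third covariate list. It stops at pre-operative haematocrit and adds: "Post-operative platelet count will also be included in all models".

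**The concern.** Models 2A and 2B and Step 4 exist to show what pre-operative Multiplate adds to what is already known about the patient. That question can be answered only if the comparator is free of pre-operative Multiplate. A covariate called platelet function, in a plan whose only pre-operative platform is a platelet function test, puts that in doubt.

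An analyst who follows footnote 6 as written could report that pre-operative Multiplate adds little or nothing simply because its information was already in the score. The same score is forced into Models 2C to 2E. Post-operative Multiplate, which repeats the same tests later, is the platform most likely to share information with that covariate, so the Step 2 choice of best platform could be affected as well.

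**Working it through.** The plan states no figure to reproduce here. The check compares the lists, traces how the score is used, and works out the consequence.

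**1. The lists side by side**

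| Item | Section 7.1 | Footnote 6 |
|---|---|---|
| Age, sex, diabetes, procedure, priority, eGFR, pre-operative haematocrit, anti-platelet group, time since withdrawal, BMI | all 10 present | all 10 present |
| Platelet item | pre-operative count | pre-operative function |
| Participation in another study | absent | present |

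Ten of the 11 items in section 7.1 reappear among the 12 in footnote 6. The eleventh differs by one word, and participation is the only addition. The SAP does not use count and function as synonyms: section 2.3 speaks of tests of platelet function and count, and section 2.6.1 places platelet count under the full blood count, apart from Multiplate.

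**2. Where the covariate goes**

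Footnote 6 → Step 1 model → single score with coefficient fixed at 1.00 (an offset) → Models 2A to 2E and their baseline-only comparator → Steps 3 and 4, which build on those models.

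**3. Consequence if the score contains a Multiplate variable M**

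Baseline fit: logit p = a + b′X + cM. Maximum likelihood gives Σ(y − p) = 0 and ΣM(y − p) = 0.

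Platform model with the fitted score S as offset: logit p = S + d₀ + d₁M. Its score equations at d₀ = d₁ = 0 are the same two sums, already zero. The log-likelihood is concave, so the maximum is at d₁ = 0. The likelihood-ratio (LR) chi-square is 0 and the AUC gain is 0.

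This is exact only for the same variable, in the same functional form, in the same sample. Step 2 considers all variables of a platform, and section 7.3 uses fractional polynomials. Other Multiplate parameters or transformations could therefore still add something, and the increment is then understated rather than abolished.

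**4. Illustration**

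Assumptions, none of them estimates from the study apart from n: n = 2400 (the planned size in section 3.1), about 25% events, one pre-operative Multiplate variable with a linear effect of 0.2, 0.4 or 0.6 log-odds per unit, both fits in the same sample, and one simulated data set per row. The post-operative proxy is correlated with pre-operative Multiplate and has no effect of its own.

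| Log-odds | Events | LR for Multiplate-pre, count in baseline | AUC gain, count in baseline | LR and AUC gain, Multiplate-pre in baseline | Proxy LR, count in baseline | Proxy LR, Multiplate-pre in baseline |
|---|---|---|---|---|---|---|
| 0.2 | 620 | 17.6 | 0.012 | 0 and 0 | 11.0 | 0.06 |
| 0.4 | 603 | 62.5 | 0.033 | 0 and 0 | 29.9 | 0.10 |
| 0.6 | 605 | 110.4 | 0.052 | 0 and 0 | 50.2 | 0.43 |

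The zeros confirm the algebra. The last two columns show that a later marker sharing the same information can lose nearly all its apparent value. Because the proxy was given no effect of its own, this is an extreme case. A post-operative result with independent information would keep that part. ROTEM and TEG were not simulated, so the relative disadvantage of Model 2C is not sized.

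**5. Post-operative platelet count**

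Section 2.7 puts it in all models. Footnote 6 does not list it, and the section 7.3 comparator holds only baseline characteristics.

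- Section 2.7 applied throughout: count is in both the model and the comparator, and no platform gains from it.
- Section 7.3 applied throughout: count is a blood count result and not a Multiplate, ROTEM or TEG measure, so it is in neither.
- Section 2.7 applied to the platform models and section 7.3 to the comparator: prediction from a routine blood count is credited to the platform.

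Only the third combination misleads, but the SAP does not exclude it.

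**The case against.** The strongest reply is that the term is a slip. Step 1 concerns patient characteristics, set apart from the test platforms, and section 7.1 shows that count was intended. Under that reading there is no circularity. The pre-operative SAP, with which the amendment log says this approach overlaps, may also define the covariate. And because Step 1 seeks an optimal model, the item might not have been retained.

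Much of this stands. A reader might infer from footnote 6 that the covariate is the pre-operative Multiplate result itself and that its increment is zero by construction. The SAP does not say the first, and the second holds only under the narrow conditions in step 3 of the working. But the reply also concedes that footnote 6 is wrong as worded, and footnote 6 is the list that builds the score.

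A reader might also infer that all three post-operative platforms are wrongly credited with the predictive value of platelet count. That needs section 2.7 to govern one side of the comparison and section 7.3 the other, which the SAP does not state. Nor do Steps 3 and 4 need a new comparator: each tests an addition to the model from the preceding step, which is the correct nested comparison.

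**Conclusion.** The discrepancy between footnote 6 and section 7.1 is certain; the circularity is conditional. If the footnote 6 item is a Multiplate measure and is retained in the score, the tests of pre-operative Multiplate in Models 2A and 2B and in Step 4 are compromised. The increment is zero for a variable entered in the same form and sample, and is otherwise understated by an amount that the SAP does not allow one to compute. Model 2C could be disadvantaged in the same way, which bears on the choice of best platform. If platelet count was meant, none of this arises. The point still needs correction, because a stated rule followed literally would spoil the comparator for every platform model. The mismatch over post-operative platelet count is a smaller, separate matter of consistency.

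**What to change.** - In footnote 6, replace preoperative platelet function by preoperative platelet count, as in section 7.1. If Multiplate was meant, remove it from the baseline score used for Models 2A to 2E and Steps 3 and 4.
- Reconcile section 2.7 with footnote 6 and section 7.3. State which models carry post-operative platelet count, and if it enters Models 2C to 2E, enter it in their baseline comparator too.
- Keep the preceding step's model as the comparator in Steps 3 and 4.
- Section 7.3 is partly written in the past tense. If the score has already been fitted, check which variable it holds.

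The cost is a few words in the SAP and, where the score holds the wrong variable, refitting the score and the models that use it.

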7.3 Model fitting

Models will be fitted first for the standard time frame. Then, models will be fitted for the rapid time frame (see [Table 2.6.3](#)), testing whether this results in a “significant” deterioration in prediction. Comparing rapid and standard time frames is interesting because there may be a trade-off between potential benefits of earlier decision making (e.g. allows definitive treatment to be provided more quickly, thereby preventing blood loss) vs. potential harms (e.g. somewhat less good prediction).

The contribution of all of these baseline characteristics to the prediction of CCB were incorporated into a single score which was forced into models of laboratory predictors with a coefficient of 1.00 in order to enable comparisons between different models based on the various laboratory test platforms.

All laboratory measures from a platform were included for each model, with multivariable fractional polynomial techniques used to investigate the linearity of terms. All transformations and centering found to improve the fit of the models were implemented. Backward elimination was undertaken to select the final models with a threshold of inclusion of 0.05 and exclusion of 0.10. Initial models only considered the standard test results (see Table 2); subsequently the ‘early phase’ alternatives were considered for any terms that significantly contributed to the model.

The following models were constructed:

- **Model 2A:** pre-operative Multiplate in relation to **any CCB**
- **Model 2B:** pre-operative Multiplate in relation to **post-op CCB**
- **Model 2C:** post-operative Multiplate in relation to **post-op CCB**
- **Model 2D:** post-operative ROTEM in relation to **post-op CCB**
- **Model 2E:** post-operative TEG in relation to **post-op CCB**

Each model was then compared to a baseline model containing only the baseline characteristics in order to evaluate the contribution of the selected laboratory test results to the prediction of CCB. These are presented as receiver operating characteristic (ROC) curves.

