3.1 Sample size

The study sample size detailed in the protocol (version 6, 21 March 2012) is 2400 which corresponds to the entire predicted patient throughput at Bristol Heart Institute for the 2 year study period, allowing for up to 10% of patients to opt-out.

Details regarding the sample size calculation and review are given in the SAP covering analyses of pre-operative test results.

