7.4.3 Analysis models

All outcomes listed in the study protocol will be presented as per the template tables [Table T7 to T8](#). General methods of presentation are outlined below.

⁷ i.e. factors associated with the both the laboratory test result(s) (exposure) and the outcome, unbalanced across the groups and not an intermediary step in the causal pathway from the exposure to outcome

The primary outcome (CCB) and secondary outcomes (any RBC transfusions > 4 units RBC transfusion, non-routine pro-haemostatic treatments, death, MI, any stroke, renal failure, AKI and infections during hospital admission) are all binary data.

These binary outcomes will be presented as numbers and percentages of patients. The association between laboratory test results and outcome will be quantified using logistic regression for binary data. Estimates will be presented as unadjusted and adjusted odds ratios (OR) and 95% confidence intervals (95% CI). For these binary outcomes analyses will only be performed if more than ten patients in total experience the outcome.

The sensitivity and specificity of laboratory test results to predict the outcome will be described for different thresholds and laboratory tests will be compared using the area under the receiver operating characteristic (ROC) curve.

The association between time of withdrawal of P2Y₁₂ blocker and laboratory test results will be described using linear regression.

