7.4.4 Statistical significance

For hypothesis tests and tests of interactions, two-tailed p-values < 0.05 are considered statistically significant. Likelihood ratio tests will be used in preference to Wald tests for hypothesis testing.

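### The question whether early-phase results predict as well as standard results has only a significance test as its criterion, with no acceptable loss, no interval and no named test

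*SAP*

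**What the plan says.** SAP 7.2 plans the same follow-up question at three points. For the best platform (Step 2), for any platform added to it (Step 3) and for pre-operative Multiplate if it is added (Step 4), the investigators will look at whether a model built on early-available variables "performs as well as a model using the standard test variables available at" test completion.

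SAP 7.3 says how: the standard-time-frame models are fitted first, then the rapid ones, "testing whether this results in a “significant” deterioration in prediction". It explains the interest as a trade-off, with earlier decisions on one side and "potential harms (e.g. somewhat less good prediction") on the other.

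Two other sections bear on this. SAP 7.4.4 states that "two-tailed p-values < 0.05 are considered statistically significant" and that "Likelihood ratio tests will be used in preference to Wald tests for hypothesis testing". SAP 7.4.3 states that "laboratory tests will be compared using the area under the receiver operating characteristic (ROC) curve", without linking that to the rapid-versus-standard comparison.

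On size, SAP 3.1 gives a sample that "is 2400 which corresponds to the entire predicted patient throughput at Bristol Heart Institute for the 2 year study period", and adds: "Details regarding the sample size calculation and review are given in the SAP covering analyses of pre-operative test results".

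**The concern.** Whether one model does as well as another is a non-inferiority question. To answer it, one needs a largest tolerable loss and evidence that the true loss is smaller. A test of no difference provides neither. If it is not significant, the loss may be nil, or the data may be too few to show it. The fewer the samples or events, the easier it becomes to reach the favourable answer.

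The plan's own reason for the comparison sharpens this. To weigh earlier decisions against poorer prediction, a reader needs the size of the loss and its uncertainty, and the stated criterion asks for neither.

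The test is also unnamed. Under Table 2.6.3 an early result replaces a standard one: velocity for Multiplate AUC, A5 or A10 for ROTEM mcf, A30 for TEG ma. Models that differ by such a swap are not nested, so an ordinary likelihood ratio test does not compare them.

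At stake is a statement that a faster reading of a platform predicts bleeding as well as the full reading, resting only on a failure to find a difference.

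**Working it through.** **What can be reproduced.** Nothing numerical. The SAP states no power, margin, expected AUC or event rate for this comparison, and the basis of the sample size is in another document. The figures below illustrate the criterion under stated assumptions.

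**Inputs.**
- From the SAP: N = 2400 (3.1), two-sided 0.05 (7.4.4). N is a ceiling, because 3.6 restricts the analysis to patients with post-operative assay results and the data that define the outcome.
- Assumed: 20% with the outcome, so n1 = 480 and n0 = 1920; AUC A = 0.70; correlation r between the two estimated AUCs of 0.80, 0.95 or 0.98.

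**Step 1: standard error of one AUC (Hanley-McNeil).** With u = A/(2 − A) = 0.5385 and v = 2A²/(1 + A) = 0.5765,

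SE² = [A(1 − A) + (n1 − 1)(u − A²) + (n0 − 1)(v − A²)] / (n1·n0)
= [0.21 + 479 × 0.04846 + 1919 × 0.08647] / 921,600
= 189.36 / 921,600, so SE = 0.01433.

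**Step 2: standard error of the paired difference.** s = SE × √(2(1 − r)).
- r = 0.80: 0.01433 × 0.6325 = 0.00907
- r = 0.95: 0.01433 × 0.3162 = 0.00453
- r = 0.98: 0.01433 × 0.2000 = 0.00287

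**Step 3: chance that a true loss d is not significant.** 1 − [Φ(d/s − 1.96) + Φ(−d/s − 1.96)].

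| True loss in AUC | r = 0.80 | r = 0.95 | r = 0.98 |
|---|---|---|---|
| 0.01 | 80% | 40% | 6% |
| 0.02 | 40% | 1% | under 1% |

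For d = 0.01 and r = 0.80: d/s = 1.103, Φ(−0.857) = 0.196, Φ(−3.063) = 0.001, giving 0.803.

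**Step 4: fewer events or samples.** For a loss of 0.02, 10% events at N = 2400 gives 63% missed at r = 0.80 and 10% at r = 0.95. With N = 1200 and 20% events the figures are 66% and 12%.

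**Step 5: which correlation is plausible.** Table 2.6.3 lists 24 standard results; 15 have no early alternative. Of the five TEG results only CK ma has one. Under 7.3 the baseline score enters the laboratory models with coefficient 1.00, and early alternatives are considered only for terms that contributed. If terms without an alternative stay in the rapid model, which the SAP does not settle, ROTEM and TEG models would overlap heavily and r would be high. For Multiplate all four AUC terms are replaced, so r could be lower. The documents do not give r.

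**Step 6: what a margin rule would achieve.** Same assumptions, true loss nil. The chance that the upper limit of a two-sided 95% interval falls below a margin m is Φ(m/s − 1.96).

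| Illustrative margin | r = 0.80 | r = 0.95 | r = 0.98 |
|---|---|---|---|
| 0.01 | 20% | 60% | 94% |
| 0.02 | 60% | 99% | over 99% |
| 0.03 | 91% | over 99% | over 99% |

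**The case against.** The strongest reply is that the SAP nowhere writes that a non-significant result means equivalence. Section 7.2 only undertakes to investigate, and 7.3 puts the word significant in quotation marks and then speaks of a trade-off. That is correct, and a reader should not infer that the plan formally declares equivalence by non-significance. What remains is that no other criterion is offered for the question 7.2 asks three times.

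A reader might also infer that the plan prescribes an invalid likelihood ratio test here. It does not: 7.4.4 states a general preference over Wald tests, and 7.4.3 names ROC area for comparing laboratory tests. The defect is that no test is assigned to this comparison. The 95% confidence intervals promised in 7.4.3 are for odds ratios, so they do not fill the gap.

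Third, nothing in the documents makes an AUC loss of 0.01 clinically relevant, and with highly correlated models at full sample size the losses that could pass unnoticed are small. Both points stand and limit the claim about size.

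Finally, the comparison is not among the objectives in 2.3 and depends on a best platform having been found. This lowers its weight, but it is still a planned comparison whose stated purpose is earlier treatment decisions.

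**Conclusion.** The concern holds as a weakness in a stated criterion. Sections 7.2, 7.3 and 7.4.4 together allow non-significance to stand in for equal performance, with no bound on the loss and no test fitted to non-nested models.

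Its size cannot be fixed from the SAP. Under the assumed event rate and AUC at the full 2400, the chance of missing a 0.01 loss runs from 80% down to 6% across the correlations considered, and for a 0.02 loss from 40% to under 1%. The risk grows with fewer usable samples or events, and is likely to be greater for Multiplate than for ROTEM or TEG if unreplaced terms stay in the model.

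It would go too far to say that a clinically relevant loss will be passed as equivalence: the plan sets no threshold of relevance, and none can be derived from it. The primary association analysis and the ranking of platforms are not affected.

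**What to change.** In 7.3, and by reference in Steps 2 to 4 of 7.2, replace the significance criterion with the following.

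- **Estimate:** AUC of the standard model minus AUC of the rapid model in the same patients, with a paired bootstrap 95% confidence interval that repeats the model selection in each resample. State whether terms without an early alternative stay in the rapid model.
- **Rule:** conclude that the rapid model performs as well only if the upper limit lies below a fixed maximum acceptable loss. The investigators state and justify this value before the comparison is run. It should not be a fraction of the AUC gain observed in the same data, because that is not a margin fixed in advance.
- **Otherwise:** report the loss and its interval as inconclusive or worse.
- **If it is too late:** 7.3 is partly in the past tense. If the comparison has already been run, or no margin can be justified, report the difference with its interval and claim no equivalence from non-significance.

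The cost is some SAP wording and a bootstrap on data already held. The drawback is that many comparisons may be inconclusive: with a 0.01 margin and no true loss, only about 20% to 60% of studies would succeed at correlations of 0.80 to 0.95 under the assumptions above.
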